## **4. SELECTION AND ENROLLMENT OF PARTICIPANTS**

### **4.1 Inclusion Criteria**

Participants must meet all of the inclusion criteria to participate in this study.

- Adults ( $\geq 21$  years of age)
- Scheduled to receive first-line Fluorouracil (5FU)-based intravenous chemotherapy treatment for a gastrointestinal cancer (stages II-IV)
- Has an Eastern Cooperative Oncology Group performance status of  $\leq 1$
- Ability to understand and the willingness to sign an informed consent document in English

### **4.2 Exclusion Criteria**

All candidates meeting any of the exclusion criteria at baseline will be excluded from study participation.

- Has a self-reported history of diagnosed sleep disorders (e.g., obstructive sleep apnea, insomnia), comorbidities associated with poor sleep or fatigue (e.g., chronic fatigue syndrome), or a job with night shifts.

### **4.3 Study Enrollment Procedures**

Individuals scheduled to receive first-line 5FU chemotherapy for a gastrointestinal cancer will be recruited from the Comprehensive Cancer Center at Wake Forest University (CCC-WFU) and the Vanderbilt Ingram Cancer Center (VICC; site-specific protocol, closed to recruitment). To identify potential patients, a study team member (STM) will screen participants using electronic medical records containing patients' schedules and communicate with attending physicians regarding patients' potential eligibility for trial. Subject recruitment will be documented in a Screening Log including reasons for ineligibility, eligible patients approached, number who declined participation, and number successfully recruited.

If the patient is interested, the STM will approach the patient at a clinic visit or call the patient to explain the protocol, answer questions, further determine eligibility, and discuss informed consent. After making sure the patient clearly understands the study

procedures and agrees to follow them, the patient will be asked to sign the informed consent form either in person or remotely (Appendix A: Informed Consent Document). If signed remotely, patients will be asked to mail, or fax the form back to us, as well as bring the original with them to their next clinic visit. A copy of the consent form will be given to the participant in person the next time they are in clinic, and the original copy will be kept in the participant's file.

Eligible participants enrolled in the study will be randomized after baseline assessments to YST or AC at week 0.

*Randomization.* Eligible, consented, and enrolled participants will be randomized to YST or AC. To control for type and stage of cancer, randomization will occur within both type (colon, rectal/other better prognosis GI cancers, poorer prognosis cancers) and stage (localized stages II/III or metastatic stage IV). Randomization (1:1) lists within each strata will be generated via a permuted block program developed and executed by the study biostatistician with blocks of random sizes between 2 and 6. The randomization lists will be held by a STM (not involved with data collection) who will allocate each participant to study group. Once assigned, details about that arm will be revealed to the PI for study coordination purposes.

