### **Sample Size and Population**

The target population is 44 participants, 22 in each group. Randomization will be stratified by type of cancer (colon, rectal/other better prognosis GI cancers, poorer prognosis cancers) and cancer stage (localized stages II/III or metastatic stage IV) to minimize differences between groups (6 strata total). We will add cancers of the small intestine, anus and appendix to our existing rectal cancer strata since the survival rates are similar. The cancer types with poorer prognoses will be put into the new strata (with <50% 5-year survival rate; cancers of the esophagus, stomach, pancreas, gallbladder, liver).

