### 6.2.1 Screening Evaluation

#### Consenting Procedure

If the patient is interested and referred by the physician, the PI or a STM will approach the patient at a clinic visit or call the patient at home to explain the protocol, answer questions, determine eligibility, and discuss informed consent (Appendix I: Recruitment Script; Appendix J: Recruitment Flyer). After making sure the patient clearly understands the study procedures and agrees to follow them, the patient will be asked to sign the informed consent form either in person or remotely. If signed remotely, patients will be asked to mail or fax the form back to us, as well as bring the original with them to their next clinic visit. If consent is obtained via REDCap, an original signature will be obtained at their next clinic visit. A copy of the consent form will be given to the participant in person the next time they are in clinic, and the original copy will be kept in the participant's file.

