#### **6.2.3 Blinding**

- Participants will be told that both groups offer programs to support their experience in coping with chemotherapy to match efficacy expectations.
- All STM will know to what arm participants are assigned. The STM collecting outcome assessments will not know which intervention each arm letter represents.
- A complete description of each study arm will be presented to participants upon their completion of all study measures (Appendix M: Thank You Letter).

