### **Treatment Assignment Procedures**

Eligible, consented, and enrolled participants will be randomized to YST or AC. To control for type and stage of cancer, randomization will occur within both type (colon, rectal/other better prognosis GI cancers, poorer prognosis cancers) and stage (localized stages II/III or metastatic stage IV). There is not a sample size goal within strata. Given this relatively small preliminary study, it was deemed more efficient and enabled tighter control over known influences on outcome to stratify rather than to use statistical control via covariate analysis. The other alternative would have been to use only a single type/stage of cancer, which was not feasible due to too few cases at VICC and CCC-WFU. The population of the cancer patients with the types/stages selected was sufficient at VICC and CCC-WFU to enable randomization within thus increasing generalizability potential.

Randomization (1:1) lists within each strata will be generated via a permuted block program developed and executed by the study biostatistician with blocks of random sizes between 2 and 6. The randomization lists will be held by a staff member (not involved with data collection) who will allocate each participant to study group. STM who are collecting data will not be informed of group assignment.

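### The protocol leaves a gap in allocation concealment: the PI learns every assignment and may also recruit, and knowing earlier assignments lets the next arm be guessed correctly about 68% of the time

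*Combined protocol and SAP*

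**What the plan says.** **The lists.** Sections 4.3 and 9.2 (Treatment Assignment Procedures) describe 1:1 lists within cancer type and stage, made by a "permuted block program developed and executed by the study biostatistician with blocks of random sizes between 2 and 6". The précis states: "The target population is 44 participants, 22 in each group", with "6 strata total". Section 9.2 adds: "There is not a sample size goal within strata". A staff member outside data collection holds the lists and allocates. Neither section says that this person is outside recruitment.

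**Who learns the arm.** Section 4.3: "Once assigned, details about that arm will be revealed to the PI for study coordination purposes". Section 6.2.3: "All STM will know to what arm participants are assigned", with only the meaning of the arm letter withheld from those who collect outcomes. Against this, 9.2 says that STM who collect data are not told the assignment, and 9.5 and 10.1 call them masked or blinded.

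**Who recruits.** Section 4.3 assigns approach, eligibility and consent to an STM. Section 6.2.1 says that "the PI or a STM will approach the patient at a clinic visit or call the patient at home to explain the protocol", and the same person determines eligibility and discusses consent. Section 11.2 again allows either the PI or an STM to hold the consent discussion. The table in 6.1 lists both for eligibility criteria, consent and enrolment/randomization. No section bars a person who knows earlier assignments from any of these steps.

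**The concern.** This is about concealment of the next assignment, which is separate from masking of outcome collection. In a permuted block the arm that is behind tends to come next. Anyone who knows a stratum's earlier assignments can see which arm that is, and an arm letter is enough to follow the sequence. If that person also decides whom to approach, how actively, and who qualifies, the expected arm can influence who enters.

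There is some room for judgement. The exclusion in 4.2 covers an open-ended class of conditions linked to sleep problems or tiredness, and 6.2.1 has research staff verify eligibility by patient interview.

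At stake is a prognostic difference between arms that would be read as a treatment effect. Section 9.2 gives informing potential efficacy as the primary purpose, and 9.6 tests at 0.05, so a biased estimate would carry into the larger trial.

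**Working it through.** The plan gives no figure for predictability. Its one numerical justification, the precision of the SD in 9.2, reproduces and is not affected by this point. The 20% lower limit of s/σ is √(χ²₀.₂₀,ₙ₋₁/(n−1)), which is 0.903 at n = 44 (9.7% below; the plan says 10%) and 0.858 at n = 22 (14.2% below; the plan says 14%).

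**Inputs.** 44 patients, 1:1, six strata (précis); "blocks of random sizes between 2 and 6" (4.3); SD 8 T-score points (9.2). Assumptions: the sizes are 2, 4 and 6, because 1:1 needs even blocks; they are equally likely; and all 44 patients enter the six current lists. The last is a simplification, since the précis says that the poorer-prognosis stratum is new.

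**Step 1: second patient in a stratum.** The first assignment is a coin flip. The probability that the second goes to the other arm is
(1/3)(1) + (1/3)(2/3) + (1/3)(3/5) = 0.756.
One known assignment moves the guess from 50% to about 76%.

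**Step 2: long list, exact.** Guess the arm that is behind and flip a coin when level. Expected correct guesses in a block of 2m are m + ½(2²ᵐ/C(2m,m) − 1).
- Size 2: 1.5
- Size 4: 2.833
- Size 6: 4.1

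The long-run rate is (1.5 + 2.833 + 4.1)/(2 + 4 + 6) = 8.433/12 = 70.3%. This guess does not require knowing the block sizes.

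**Step 3: this trial, simulated** (1,500 trials per six-stratum or 12-list setting).
- The stratum is unbalanced at 55% of enrolments (about 24 of 44), and the guess is then right 82.4% of the time.
- Overall: 0.45 × 0.50 + 0.55 × 0.824 = 0.678, or about 30 of 44 correct. Concealment gives 22 of 44.
- An exact calculation of the next-arm probability for someone who knows the possible sizes gives the same 68%.
- The next arm is certain at 2.7% of assignments (about 1.2 of 44).

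**Step 4: sensitivity.**

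| Setting | Correct guesses | Certain |
|---|---|---|
| Six equal strata, sizes 2, 4, 6 | 68% | 2.7% |
| Six uneven strata, sizes 2, 4, 6 | 68% | 2.7% |
| Six strata, sizes 2 and 4 only | 70% | 9% |
| 12 lists (six strata at two sites) | 65% | 1.3% |
| One unstratified list | 70% | 4% |

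More strata lower the rate slightly, because more lists stop in mid-block.

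**Step 5: illustration of bias.** Suppose patients enrolled when YST is expected differ by g points from those enrolled when AC is expected, with no selection when the stratum is level. With no treatment effect, the arms then differ by
g × 0.55 × (0.824 − 0.176) = 0.356g.
For g = 2 this is 0.71 points; for g = 4, 1.43 points. The documents give no value for g.

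For scale, 0.71/8 = 0.09 SD. The standard error of the difference at 22 per arm is 8√(2/22) = 2.41, so 0.71 points is about 0.3 standard errors.

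**The case against.** The case on the other side has substance.

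- **The PI's role is permissive.** Section 4.3 names only an STM, and 6.2.1 and 11.2 say one or the other. A reader might infer that the PI is the designated recruiter, or that enrolment was steered. The documents show neither. The permission, and the disagreement between sections, remain.
- **Whether STM know the arm is unresolved.** Section 6.2.3 cannot be taken alone against 9.2, 9.5 and 10.1. Those sections protect data collection, however, and do not mention recruitment.
- **There are checks.** They include physician referral (6.2.1), oncologist permission (6.1) and a Screening Log of refusals and reasons for ineligibility (4.3). A registrar requires eligibility source documents (6.2.2), and eligibility compliance is reviewed (7.6, 10.3.2). These limit discretionary exclusion and make it visible, but do not conceal the next arm.
- **Room to manoeuvre is limited.** Most criteria in 4.1 are objective, and the exclusion in 4.2 rests on self-reported history. Timing follows chemotherapy (6.2). At 1 to 2 patients per month (9.4), an evenly filled stratum gains one patient every 3 to 6 months (6/2 to 6/1), so holding a patient back for a preferred arm is unrealistic. What remains is whom to approach, how actively, and borderline eligibility.
- **Baseline fatigue is measured before randomization (4.3), and 9.6 models change from baseline.** A reader might conclude that no analysis could repair the damage. That is too strong: selection on entry fatigue is recorded and at least partly handled. Selection on unrecorded prognosis or motivation is not.
- **The illustrated bias is small and hypothetical.** This is correct, and it is why the figure serves only as an illustration.

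**Conclusion.** The concern holds as a gap in allocation concealment that the protocol permits. A person who knows earlier assignments may recruit, and would guess the next arm correctly about 68% of the time instead of 50% (65 to 70% across the settings tried). This rests on block sizes 2, 4 and 6 being equally likely and on the recruiter knowing the stratum's earlier assignments.

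Two further inferences are not supported. First, the next arm is not usually known: varying block sizes leave only about 3% of assignments certain. Second, the six strata do not cause the problem, since a single list is slightly more predictable. The drivers are small blocks combined with known past assignments.

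The residual risk is mainly selection on prognosis that is not recorded. Its size depends on behaviour that the documents cannot show. The point merits correction because the remedy is cheap, not because bias has been demonstrated.

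**What to change.** - In 4.3, 6.1, 6.2.1 and 11.2, state that approach, eligibility confirmation and consent are done only by STM with no access to earlier assignments, including arm letters, and that the PI and the list holder take no part in these steps.
- Reconcile 6.2.3 with 9.2, 9.5 and 10.1, so that knowledge of the arm is limited to the interventionists, the PI and the list holder.

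The PI can still be told assignments for coordination. Removing the block sizes from the protocol would not be enough, since the guess in step 2 does not use them. No new rule on release of assignments is needed: 4.3 already randomizes only after eligibility and consent, and 6.2.2 already requires registration.

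For recruiters, the guess rate falls to 50%. Sample size, alpha, visits and interventions do not change. STM may already perform every recruitment step, and those who collect data are already meant to be masked, so no new post is implied, although the documents do not give STM numbers. The downside is that the PI can no longer consent patients personally, which makes scheduling slightly less flexible.

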## 5. STUDY INTERVENTIONS

### 5.1 Interventions, Administration, and Duration

**Active Intervention.** The Yoga Skills Training (YST) intervention will be administered individually in the outpatient clinic while patients are in the chair during outpatient chemotherapy sessions and patients will be encouraged to practice the YST daily at home. First-line 5FU-based chemotherapy for gastrointestinal cancers is typically given during biweekly visits. [name] developed the YST for a prior study to teach the key elements of yoga in a manner that would accommodate patients' needs and reduce barriers to adherence during chemotherapy. The YST intervention consists of four 30 minute in-person sessions (weeks 2, 4, 6, 8) that instructs skills to enhance mindfulness and promote relaxation: (a) *Awareness* – noticing the current state and establishing relaxed breathing – 5 minutes; (b) *Movement* - 7 minutes of gentle movements coordinated with the breath (such as raising and lowering the arms); (c) *Breathing Practice* - 3 minutes of inhaling cool air as if through a straw; (d) *Meditation* - 5 minutes of focus on letting go of physical and mental tension. In addition, the first five minutes of the YST will address any questions and inquire about the participant's current physical status. The last five minutes will be used to review a handout describing the YST (Appendix B: YST Home Practice Guide; Appendix C: YST Diary) and to encourage participants to practice daily with strategies to increase adherence to home practice described later in this section. Participants will also be given an audio recording of the YST and devices to play the recording. The content of the YST was informed by [name] training from the Integral Yoga Academy's Yoga for People with Cancer Teacher Training taught by [name], RYT, the Urban Zen Integrative Therapy training, and was modified for this study to further target fatigue and depressive symptoms by

consulting with expert yoga therapists from the Krishnamacharya tradition (i.e., led by [name]). Each session will contain the same content, but the movement will be individualized based on ability and level of energy that day. Self-compassion will be highlighted throughout the YST and any medical restriction can be accommodated. All yoga instructors (i.e., interventionists) will have completed accredited yoga teacher training programs and be experienced teaching patients with chronic illness. Minimal risk including potential for muscle soreness from the gentle movements or emotional discomfort from breathing and meditation practices is expected from participating in the YST.

**Attention Control (AC).** An empathic attention control group will be employed as the AC to account for the added attention and efficacy expectations of the YST as used in previous studies. In addition, the interventionist will recommend that the patients write brief diary entries daily at home as used as a control condition in another previous study (Appendix D: AC Home Diary). The AC will not include instruction of movement, meditation or breathing practices, which are the active ingredients of the YST. The location, number of sessions with a professional, recommended home practice, and home assessments will also be matched to the YST. The AC will be implemented by an individual with a background conducting research in a medical setting who will be trained to create and maintain a relationship by using techniques of active listening, reflection of statements, and avoiding negative judgments. This individual will spend approximately 30 minutes with patients for four sessions while they are undergoing chemotherapy. S/he will utilize standardized instructions to prompt the patient as adapted from previous studies: “What were some of the events or circumstances that affected you in the past two weeks?” Patients will be encouraged to “discuss one experience at a time, even if it means talking about the same experience each session. However, if you find that you have discussed it in adequate detail, please move on to a new topic.” The instructions for daily diary entries will be, “What were some of the events or circumstances that affected you in the past day? Think back over the past day and write down on the lines below up to five events that had an impact on you.” Minimal risk including potential for emotional discomfort from disclosing personal experiences is expected from participating in the AC.

## 5.2 Handling of Study Interventions

Participants will be told that both groups offer programs to support their experiences in coping with chemotherapy to match efficacy expectations. Information about both arms will be revealed to participants after completion of data collection.

**Treatment Fidelity.** A number of steps will be taken to ensure treatment fidelity. [name] will train interventionists in implementation of the YST and AC during an initial four hours of training and monthly meetings. [name] will remain an objective observer in order to develop a system for establishing treatment fidelity. One primary YST and AC interventionist will implement the interventions and at least two additional interventionists trained in the intervention protocol will serve as back-ups. The interventionists will complete a written test to confirm their understanding, be

video recorded during all sessions (using a small device that will not record the patient or anyone else present) with 10% of the recordings randomly selected for [name] review, and document each in-person session with a checklist (Appendix E: Treatment Fidelity Forms). The checklist will be also used to evaluate consistency of implementation.

**Adherence Strategies.** To optimize adherence to home practice interventionists will be trained to adopt brief coaching methods based on motivational interviewing as used to encourage yoga practice and walking in other studies of cancer patients. Specifically, the interventionists will ask open-ended questions to inquire about goals, specific times planned for home practice, and strategies to ensure home practice of the interventions. Confidence in the ability to practice will be verbally assessed and reports of low confidence discussed.

## **5.3 Concomitant Interventions**

### **5.3.1 Allowed Interventions**

All participants will continue with routine treatment of medical conditions including chemotherapy and medications.

### **5.3.2 Required Interventions**

No additional interventions are required except for those proposed in the protocol.

### **5.3.3 Prohibited Interventions**

There will be no prohibited medications among patients in this study. Prior approval of participation in other behavioral intervention studies is required.

## **5.4 Adherence Assessment**

Adherence will be assessed by: (1) participation in-person sessions (i.e., number of sessions completed); (2) number of components completed at each in-person YST session; (3) and days of intervention home practice (see Section 6.2 - Description of Evaluations). Instructors will directly observe and document adherence to in person sessions. We will consider high adherence to protocol if participants complete 75% of the planned in-person sessions and 3 or more days of home practice per week in between in-person sessions.

# **6. STUDY PROCEDURES**

## 6.1 Schedule of Evaluations

Assessment	Screening: (Day-14 to Day -1)	Consent Enrollment, Randomization (Day 0)	Daily Survey (W0-W2)	AC or YST 1 (W2)	AC or YST 2 (W4)	AC or YST 3 (W6)	AC or YST 4 (W8)	Daily Survey (W8-W10)	(W10)	Follow-up (W14)	Person(s) Responsible
Inclusion/Exclusion Criteria	X										PI, STM
Permission of Oncologist	X										PI, STM
Informed Consent Form		X									PI, STM
Enrollment/Randomization		X									PI, STM
Demographics		X									STM
Clinical Data		X								X	STM
Questionnaire		X					X		X	X	STM
Automated Daily Survey			X					X			Participant
Actigraphy			X					X			Participant
Treatment Fidelity				X	X	X	X				PI, Interventionist
Intervention Home Practice						X		X			Participant
Adherence		X	X	X	X	X	X	X	X	X	PI
Blood Draws				X					X		STM
Adverse Events				X	X	X	X				Interventionists, A PI, B STM C
Interview										X	Trained Facilitator

**Note.** AC = Attention Control; YST = Yoga Skills Training; PI = Principal Investigator; STM = Study Team Member

A Interventionists will note any adverse events that occur during the intervention or reported by patients during home practice.

B The PI will review interventionists' notes and identify any AE's that need to be captured.

C Other Study Team Members (e.g., Research Nurses) will report ratings of 3 or higher on the suicide item from the depression assessment (corresponding with Weeks 0, 8, 10 and 14). They will not collect any additional information related to adverse events.

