### Active Control

- Emotional discomfort

Expected adverse experiences to the participant related to assessment are as follows:

- Bruising or minor swelling
- Emotional discomfort

Each interventionist will monitor and note any adverse events experienced during the interventions (e.g., patients' experience of disturbed breath, expression of physical/emotional discomfort, or request to discontinue the in-person intervention sessions). In addition, interventionists will ask participants if they experienced any problems when doing the home practices and review notes from the home practice logs. These logs will be reviewed by the interventionist at each in-person session.

If a participant reports a 3 (sometimes) or higher on the item, "I thought about suicide" from the standardized PROMIS-Cancer Depressive symptoms short-form, we will inform the participant's oncologist regarding concern for depression and need for further evaluation from a mental health specialist (psychiatrist and/or clinical psychologist) within 24 hours of receiving the questionnaire (all implemented in person with the exception of the follow-up, which may be returned by mail). We will also notify oncologists if their patient verbally reports severe depressive symptoms or suicidality during the course of the study to research staff.

Two or more adverse events attributable to the interventions will prompt modification of the protocol.

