**‘Expectedness’: AEs can be ‘Unexpected’ or ‘Expected’ for expedited reporting purposes only.**

- **Attribution** of the AE:

- Definite – The AE **is clearly related** to the study intervention.
- Probable – The AE **is likely related** to the study intervention.
- Possible – The AE **may be related** to the study intervention.
- Unlikely – The AE **is doubtfully related** to the study intervention.
- Unrelated – The AE **is clearly NOT related** to the study intervention.

SAEs unequivocally due to disease progression are not considered SAEs for the purposes of this study and will not be reported as such.

Only AEs related to the study intervention or measures will be captured with the exception of unexpected grade 4 Grade 5 events, which will also be documented and reported.

AEs will be labeled according to severity, which is based on their impact on the patient. An AE will be termed “mild” if it does not have a major impact on the patient, “moderate” if it causes the patient some minor inconvenience, and “severe” if it causes a substantial disruption to the patient’s well-being.

AEs will be categorized according to the likelihood that they are related to the study intervention. Specifically, they will be labeled definitely unrelated, definitely related, probably related, or possibly related to the study intervention.

Interventionists will document and report solicited AEs including physical or emotional discomfort. STM will also document self-reported ratings of 3 or higher on the suicide item from the PROMIS-Cancer Depressive symptoms measure. No additional unsolicited events will be systematically captured. Research staff will report AEs according to data safety monitoring plan. Events will be documented in the ORIS data entry system including date of event which will avoid double capture.

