## **7.5 Follow-up for Adverse Events**

AEs will be monitored by the IMC and the PI for recurrences, resolution, and ongoing toxicities that may be related to the intervention. Documentation and reporting for follow-up AEs will occur according to reporting procedures described in Section 7.4. The duration for follow-up will be for the length of the study period while participants are enrolled in the study. If non-serious adverse events are related to the interventions, then the protocol will be modified to avoid adverse events. If the frequency of non-serious adverse events is higher than anticipated or alters the benefit risk ratio, the study investigators, after conferring with IMC, will also modify the protocol. Two or more specific adverse events among participants will prompt modification of the protocol.

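### After the Week 8 session no adverse-event enquiry is scheduled beyond the suicide item and grade 4/5 events, and Section 6.1 gives no one the task of recording harms caused by assessments

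*Combined protocol and SAP*

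**What the plan says.** Section 7.3 sets the scope: "Only AEs related to the study intervention or measures will be captured". It then adds certain grade 4 and grade 5 events, which Section 7.4 sends for review whatever their cause. Section 7 lists the expected effects of assessment as bruising, slight swelling and emotional discomfort. For the interventions it lists emotional discomfort in both arms and muscle soreness in the yoga arm.

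In Section 6.1 the Adverse Events row is marked in the four session columns only. The footnotes divide the work:

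- Footnote A, interventionists: "Interventionists will note any adverse events that occur during the intervention or reported by patients during home practice".
- Footnote B: "The PI will review interventionists' notes and identify any AE's that need to be captured".
- Footnote C, other team members: they report suicide-item ratings of 3 or above at Weeks 0, 8, 10 and 14. Beyond that, "They will not collect any additional information related to adverse events".

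The same table assigns the blood draws (Weeks 2 and 10) and the questionnaires (Weeks 0, 8, 10 and 14) to study team members.

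On home practice, Section 7 has interventionists ask about problems and look through the paper logs: "These logs will be reviewed by the interventionist at each in-person session". Section 6.2 has the automated survey record minutes practised each day for two weeks after the last session. Section 7.3 adds that other unsolicited events are not collected systematically. Section 7.5, on following up adverse events, says "The duration for follow-up will be for the length of the study period while participants are enrolled in the study".

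**The concern.** Exposure continues after the last enquiry. Participants are still expected to practise, and are asked daily how long they practised, up to Week 10. The second study blood draw is also at Week 10. By then the interventionists, who are the only people asked to look for general adverse events, have finished their sessions. The investigator works from their notes, and the staff present at Week 10 are told to collect nothing but the suicide item.

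At stake is the completeness of a small count with consequences. Sections 7, 7.5 and 9.4 each require the protocol to be modified once two or more adverse events occur, in slightly different words. At that threshold one or two unrecorded events can decide whether the trigger is met. Section 7.6 also requires an annual statement on whether event rates match pre-study assumptions, and Section 3 says the pilot is meant to inform a larger trial.

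**Working it through.** The plan gives no figure to reproduce here. The check compares the schedule with the scope statements.

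**Inputs**

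- General adverse-event enquiry (Section 6.1 row): Weeks {2, 4, 6, 8}.
- Suicide item (footnote C): Weeks {0, 8, 10, 14}.
- Study blood draws (Sections 6.1 and 6.2): Weeks {2, 10}.
- Questionnaires (Section 6.1): Weeks {0, 8, 10, 14}.
- Tracked home practice (Section 6.2): paper logs during the intervention, from Week 2, then the daily survey to Week 10.
- Last log review (Section 7): the Week 8 session.

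**Step 1. Weeks with any scheduled capture.** {2, 4, 6, 8} together with {0, 8, 10, 14} gives {0, 2, 4, 6, 8, 10, 14}. At Weeks 0, 10 and 14 this is the suicide item alone.

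**Step 2. Blood draws with no general enquiry at the visit or later.** {2, 10} minus {2, 4, 6, 8} leaves {10}: 1 of 2.

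**Step 3. Home practice after the last log review.** Tracked practice lasts 10 − 2 = 8 weeks. The part after the last review is 10 − 8 = 2 weeks, and 2/8 = 25%.

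**Step 4. Existing contacts where the gap could be closed.** Questionnaire visits after Week 8 are Weeks 10 and 14.

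**Step 5. Who would record each in-scope event?**

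| Event | Route in the plan |
|---|---|
| Discomfort at a session, or home-practice problem up to Week 8 | Interventionist (footnote A) |
| Suicide item rated 3 or above | Team member (footnote C) |
| Unexpected grade 4, any grade 5 | Sections 7.3 and 7.4 |
| Effect of the Week 2 draw | No one named in Section 6.1; could be raised at a session, since Section 7.3 does not limit solicited discomfort by cause |
| Home-practice problem, Weeks 8-10 | None assigned; the survey item described asks only for minutes |
| Effect of the Week 10 draw | None assigned; footnote C excludes the staff responsible |

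The last two rows are the gap. The events that Section 7 expects (soreness, discomfort, bruising, swelling) are mild, so the grade 4/5 route would not pick them up.

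**The case against.** The best defence is that limited collection is deliberate. Section 7.3 restricts which events count; it does not promise active questioning at every visit, and it says openly that unsolicited events are not gathered systematically. Section 7.2 describes minimal risk and reports no intervention-related events in two earlier pilots, of 7 and 15 participants. Study samples are taken alongside routine clinical draws, so they add little harm. The revision history says the schedule footer was changed to match the data safety and monitoring plan, which is not among the documents. The final interview, with 20-40 participants, might also bring problems to light.

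This lowers the importance of the point but does not remove it. A restriction to related events still needs someone to record the related events that are expected, and for two kinds no one is named. The interview is not an adverse-event instrument and does not reach everyone.

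Several stronger readings are tempting, and the documents do not support them:

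- *Events are collected only at the four sessions.* Footnote C and the grade 4/5 route show otherwise. Oncologists are also told of severe depressive symptoms or suicidality reported verbally to staff. For the same reason, calling Weeks 8-14 (6 of the 12 weeks from first session to final visit) free of any enquiry overstates the gap.
- *Section 7.5 demands detection through Week 14.* It concerns recurrence, resolution and continuing toxicity of events already identified.
- *These harms cannot be captured.* A spontaneous report could still be recorded; what is missing is an assigned route.
- *The yoga arm is under-counted more.* Muscle soreness is listed only there, so this is plausible. But the control arm also has home practice and expected emotional discomfort, and nothing in the documents gives the difference a size.
- *Missed draw effects distort every trigger.* The Section 7 trigger covers events attributable to the interventions, so bruising from a draw does not enter it. The wording in Sections 7.5 and 9.4 is less specific.

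**Conclusion.** The concern holds in a limited form. Apart from the suicide item and the grade 4/5 route, no adverse-event enquiry is scheduled after the Week 8 session, and Section 6.1 gives no role the harms caused by assessments. The affected exposure is 2 of 8 weeks of tracked home practice and 1 of 2 blood draws. The count behind the safety report and the modification triggers is incomplete to that extent. The number of events lost cannot be estimated from the documents and is probably small, given the mild effects expected.

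This rests on three assumptions: all four sessions take place, with the last at Week 8; the daily survey carries no symptom-problem question beyond what Section 6.2 describes, since the appendix content is not shown; and the separate monitoring plan adds no further enquiry. The change is worth making because it is cheap and improves a count that feeds a low threshold.

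**What to change.** 1. Mark Adverse Events at Weeks 10 and 14 in Section 6.1.
2. At those visits add a short self-report item, worded identically in both arms and naming neither intervention. It should ask about problems from the programme, home practice or study measures since the last enquiry.
3. Keep it apart from the questionnaires handled by masked staff. Have it completed separately or through REDCap and read only by the principal investigator, who already knows the allocation under Section 4.3, or by an unmasked team member. A free-text answer on the main form could reveal the arm to outcome collectors, whom Sections 9.5 and 10.1 describe as masked.
4. Name who records draw-related events at Weeks 2 and 10.
5. Reconcile footnotes A to C with Sections 7 and 7.3 so that scope and assigned roles agree.

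The cost is one or two items at two existing visits and slightly more adverse-event review. No extra visit or staff member is needed.
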